- 1. Safety: The safety of LAU-7b therapy will be assessed through the monitoring of treatment emergent adverse events and serious adverse events, vital signs including oxygen saturation and body temperature, symptom-directed physical examinations and safety laboratory tests. It is important to note that most of these assessments are also SOC for hospitalized patients with COVID-19 disease and changes from baseline can depict improvement or worsening of the condition.
- 2. Efficacy: Rate of all-causes death, depicted by a change from baseline in the ordinal scale position to category 7 by Days 29 and 60, compared between the active and control (placebo) arms of the study.
- 3. Efficacy: Rate of COVID-19 disease-related transfer to mechanical ventilation or ECMO, depicted by a change from baseline in the ordinal scale position to category 6, compared between the active and control (placebo) arms of the study.
- 4. Efficacy: Proportion of patients alive and free of respiratory failure by Day 29 (ordinal scale scores 1-4, inclusively), compared between the active and control (placebo) arms of the study.
- 5. Efficacy: Proportion of patients re-hospitalized after discharge (any stay in the hospital of minimum overnight duration, all causes) up to Day 60, compared between the active and control (placebo) arms of the study.
- 6. Efficacy: Rate of COVID-19 disease-related aggravation, depicted by a change from baseline in the ordinal scale position of at least one category, compared between the active and control (placebo) arms of the study.
- 7. Efficacy: Rate of COVID-19 disease-related transfer to ICU, compared between the active and control (placebo) arms of the study.
- 8. Efficacy: Patient status on the 7-point ordinal scale on Days 14 and 29; compared between the active and control (placebo) arms of the study.

Study Endpoints

(cont'd)

9. Efficacy: Mean change from baseline of the ordinal scale patient status as a function of assessment time, compared between the active and control (placebo) arms of the study.

10. Efficacy: Time to an improvement of one category on the ordinal scale patient status, compared between the active and control (placebo) arms of the study.

11. Efficacy: Time to recovery, defined here as a move from baseline to categories 2 or 1 on the ordinal scale patient status (first occurrence if more than one), compared between the active and control (placebo) arms of the study.

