9.2 Study Visits and Procedures

9.2.1 Screening and Eligibility Assessments (Visit 0, pre-randomization on Day -1 or (no Day 0 in this study)):

Prior to randomization, potentially eligible and interested patients will undergo the following:

- 1. Verification of identity and age;
- 2. Prior to any study specific screening activities, all potential patients will sign the Study Informed Consent Form (ICF), since paper copies are deemed contaminated, it is possible to take a picture of the signed page when possible. The consent can also be obtained verbally per COVID-19 regulatory requirements or local recommendations and use a witness to attest of the verbal consent. The consent forms will comply with all applicable regulations governing the protection of human subjects. An ICF Form, approved by Laurent Pharmaceuticals and the site's institutional review board (IRB or REB, as applicable), must be used. At this point, the patient's initials are used for identification purposes and to identify the patient at the time of randomization in the IWRS. The IWRS will issue the Subject Number (Randomization Number); it will be used from that point forward for the entire study participation, to identify the patient.
- 3. Verification of all inclusion and exclusion criteria:
- 4. Obtain demographic information and recent & relevant medical history (typically the previous 6 months). Particular attention will be put on confirming the underlying disease or factors (including COVID vaccination) susceptible to affect the prognosis of COVID-19 disease progression and used to determine eligibility;
- 5. Verification of the concomitant medications, including any supplemental oxygen currently in use, along with recording the oxygen flow in use;
- 6. Body weight, height, with BMI calculated (measured if possible but self-reporting is accepted);
- 7. Directed physical examination (symptom- and disease-driven);
- 8. From SOC, collect the vital signs including heart rate, respiratory rate, oxygen saturation (under room air if possible, or value obtained prior to administering supplemental oxygen, from patient chart) and body temperature;
- 9. COVID-19 symptom check (including but not limited to, fever, myalgia, coughing, dyspnea, smell and taste alteration, headache, gastrointestinal disorders...etc.) as per SOC;

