9.2.1.1 Repeat performance of screening assessment(s)

Repeat of individual screening assessment(s) that did not meet eligibility criteria is not permitted unless there is clear and documented evidence of a laboratory error (e.g., hemolyzed sample) or equipment malfunction. If the repeat values of the individual assessment(s) are within the eligibility criteria and completed before randomization, then the patient is eligible for the study.

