9.2.3 In-Hospital Days

For this study in hospitalized patients with confirmed COVID-19 disease, the hospital stay duration will vary as a function of complications/improvement observed with each given patient, the bed and resources availability, rules and restrictions imposed by Health Authorities (Institution, Governmental...etc.). In order to minimize the burden of this study on the hospital resources, the in-hospital study requirements will piggyback on the SOC, with some exceptions. The overall scheme can be found in the Schedule of Event on page 11. Details are presented below.

1. Pre-Dose on Day 4 only:

If the patient has tolerated the Initial treatment of 3 days, if not done previously, a replenishment will be requested in the IWRS and the Follow-up treatment container (22 capsules) will be retrieved from the pharmacy (where applicable) and stored in the ward's refrigerator.

- 2. On Days 5, 8 and 12 (visits 5, 8 and 12, with a window of +/- 1 day while in hospital), the following assessments will be done:
 - a. Concomitant medication verification, including any supplemental oxygen currently in use;
 - b. Directed physical examination (symptom- and disease-driven);
 - c. From SOC, collect the vital signs including heart rate, respiratory rate, oxygen saturation and body temperature (can be done multiple times during each day as part of SOC, but at a minimum twice);

- d. COVID-19 symptom check (including but not limited to, fever, myalgia, coughing, dyspnea, smell and taste alteration, headache, gastrointestinal disorders...etc.) as per SOC;
- e. SOC laboratory tests including at a minimum, urinalysis (dipstick), hematology and serum chemistry, as per Section 11.2 (the laboratory test can be performed within +/- 1 day from the target visit day);
- f. Health status determination using the 7-point ordinal scale;
- g. Handing study medication for intake during the main meal of the day;
- h. Asking safety-focused open-ended questions:
 - i. How is your health today?
 - ii. How is your vision today?
 - iii. How is your skin today?
- i. Adverse event verification and follow-up on ongoing adverse events.

3. On Day 14 or on the Day of hospital discharge (not a preset visit number), the following assessments will be done:

- a. Concomitant medication verification, including any supplemental oxygen currently in use;

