11.3 Vital Signs and Physical Examinations

Consistent with the site's SOC, vital signs, directed Physical Examinations will be performed according to the Schedule of Events, page 11, and will be symptom- or disease-driven. After screening, any clinically significant abnormal findings in physical examination should be reported as AEs.

^{*} If urine is positive for leukocyte esterase, nitrite, urobilinogen, protein, or blood, if part of SOC, microscopic examination of urine will be performed for leukocytes, erythrocytes, crystals, bacteria, and casts, as per SOC.

Vital signs include blood pressure (systolic and diastolic), temperature (oral or tympanic, consistently determined being a key COVID-19 sign), pulse rate, oxygen saturation and respiratory rate. Oxygen saturation may be performed while the patient is stabilized on room air, in the view of determining if oxygen supplementation is needed.

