12 STATISTICAL ANALYSIS

A statistical analysis plan (SAP) will provide details of the methods of analysis to address all study objectives. The SAP may be amended during the course of the study, but will be finalized before the cutoff date for any analysis, interim or final.

Data summaries by treatment group will be presented. For categorical data such as the 7-point Ordinal Scale, data will be tabulated in frequency tables to display the number and proportion of patients for each category by treatment group. For continuous variables, data will be summarized with the number of patients, mean, standard deviation, median, and minimum and maximum values by treatment group. Baseline assessments for each outcome variable will be defined as the screening measurement unless a repeat value was obtained, see restrictions in Section 9.2.1.1, before the first dose of study drug. Statistical significance will be set at the 5% level (one-sided) for the pilot portion and at the 5% level (two-sided) for the extension. Consideration

will be given for adjusting for pre-specified prognostic baseline factors such as age, the ordinal scale health status at baseline and comorbidities, where applicable.

Diligent efforts will be made to prevent missing data in the study. For example, patients who discontinue the study treatment early should still be followed for all regularly scheduled visits for safety and relevant efficacy assessments, until the Day 60 follow-up. A clear distinction should be made between treatment discontinuation and study withdrawal. Efficacy assessments occurring after treatment discontinuation should not be included in the per-protocol analysis.

Database lock and statistical analyses will be performed for the pilot portion and the extension, separately.

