12.8.3 Vital Signs

Vital signs (blood pressure, temperature, heart rate, oxygen saturation and respiration rate) will be presented at each time point using descriptive statistics (mean, standard deviation, median, minimum, and maximum). Change from baseline values for each variable will also be presented by treatment group.

The number and percentage of patients that meet the abnormal criteria for with shift changes from baseline of the vital signs during the TEAE period will be presented by treatment group. The specific changes of interest are:

- Diastolic Blood Pressure ≤45 mmHg and decrease from baseline ≥10 mmHg, Diastolic Blood Pressure ≥110 mmHg and increase from baseline ≥10 mmHg;
- Systolic Blood Pressure ≥160 mmHg and increase from baseline ≥20 mmHg, Diastolic Blood Pressure ≤45 mmHg and decrease from baseline ≥10 mmHg;
- Temperature ≤35°C and ≥38°C
- Heart rate ≤50 bpm and decrease from baseline ≥20 bpm, heart rate ≥120 bpm and increase from baseline ≥20 bpm;
- Oxygen saturation values and respiratory rate determined by the Investigator to be clinically abnormal (and reported as an AE). More specifically, the incidence of oxygen saturation being 92% or lower when measured in patient stabilized on room air, will be presented by treatment group.

No statistical analyses of vital signs are planned.

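### The change-from-baseline table for oxygen saturation compares a baseline taken off oxygen where possible with later readings that may be on oxygen; a minor flaw confined to a descriptive safety table, with a cheap remedy

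*Protocol*

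**What the plan says.** Protocol Section 9.2.1 sets a condition on the screening reading: "oxygen saturation (under room air if possible, or value obtained prior to administering supplemental oxygen, from patient chart". Section 12 makes that value the baseline: "Baseline assessments for each outcome variable will be defined as the screening measurement unless a repeat value was obtained". Section 12 refers to Section 9.2.1.1 for limits on repeats; there, repeating a screening assessment that failed eligibility "is not permitted unless there is clear and documented evidence of a laboratory error" or equipment malfunction.

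The in-hospital instruction in Section 9.2.3 sets no such condition: "From SOC, collect the vital signs including heart rate, respiratory rate, oxygen saturation and body temperature". This applies on Days 5, 8 and 12, on the other hospital days, and at Day 14 or discharge. Section 11.3 makes room air optional: "Oxygen saturation may be performed while the patient is stabilized on room air, in the view of determining if oxygen supplementation is needed".

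Section 12.8.3 lists oxygen saturation among the vital signs and says: "Change from baseline values for each variable will also be presented by treatment group". It neither restricts nor stratifies that summary by oxygen use. The same section limits a separate summary, the incidence of saturation at 92% or lower, to readings on room air, and says that vital signs will not be tested statistically. On safety assessments in general, the Synopsis says that "changes from baseline can depict improvement or worsening of the condition".

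**The concern.** Saturation depends on both lung function and the oxygen being given. Subtracting a value deliberately taken off oxygen from one that may be taken on oxygen combines the two. Patients enter at score 3 (no oxygen) or score 4 (on oxygen), so the mixture is present from the start and changes as patients are weaned or deteriorate.

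Oxygen use after randomisation is part of the disease course that the drug is meant to alter. Randomisation balances it at entry but not afterwards, so if treatment changes oxygen need, the artefact need not cancel between arms. At stake is whether a reader of the safety table, told that such changes can show improvement or worsening, takes a difference in oxygen delivery for a difference in lung function.

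**Working it through.** The plan states no figure to reproduce. The check sets the measurement conditions side by side and then sizes the consequence on assumed values.

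**Measurement conditions**

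- Baseline: room air if possible, otherwise the pre-oxygen chart value (Sections 9.2.1 and 12).
- In hospital: routine-care reading, no condition stated (Section 9.2.3); room air optional (Section 11.3).
- Oxygen at entry: none at score 3, supplemental oxygen at score 4 (Sections 7.1.1 and 8.1).
- Planned summary: later value minus baseline, by arm, regardless of oxygen (Section 12.8.3).

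That later readings are taken on whatever oxygen is in use follows from the absence of a condition; no sentence says it outright.

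**Single patients (assumed saturations)**

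- Score 4, pre-oxygen 90%, later 94% to 96% on oxygen: 94 − 90 = +4 to 96 − 90 = +6, with no change in lung function.
- Score 3, 94% on room air, worsens to score 4 and reads 94% to 96% on oxygen: 94 − 94 = 0 to 96 − 94 = +2, although the ordinal score has worsened.

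**Arm means**

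Let *d* be the points that oxygen adds, *p* the share of an arm's readings taken on oxygen at a visit, and *q* the share of its baselines taken on oxygen despite the room-air preference. With *d* constant:

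mean observed change = mean room-air change + *d* × (*p* − *q*)

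Randomisation makes *q* equal between arms in expectation, so:

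shift in the between-arm difference = *d* × (difference in *p* between arms)

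Assume *d* = 3 to 6.

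- Within one arm, with *q* = 0 and *p* = 0.5 to 0.9: 3 × 0.5 = 1.5 to 6 × 0.9 = 5.4 points.
- Between arms, for a 10-percentage-point difference in *p*: 3 × 0.10 = 0.3 to 6 × 0.10 = 0.6 points, towards the arm using more oxygen.
- Between arms with equal oxygen use: 0.

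The within-arm figure is the larger one, but it is not a bias in the treatment comparison. The between-arm figure is the relevant one.

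**The case against.** The strongest reply is that little depends on this table. Section 12.8.3 plans no tests of vital signs and no decision is tied to them. Ventilation or death by Day 60 is unaffected, and so are the ordinal-scale endpoints, which capture oxygen need directly. The one saturation threshold that the section singles out is already limited to room air. All of this stands and sets the severity. It does not repair the change table, and the room-air incidence says nothing about patients who have no room-air reading.

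A reader might infer more than the documents support:

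- *That the table will point against the better arm.* This depends on the values chosen. From a pre-oxygen 88%, a patient at 95% on oxygen shows 95 − 88 = +7. The same patient weaned to room air shows 94 − 88 = +6 at 94%, but 96 − 88 = +8 at 96%. A reversal also requires the true room-air difference to be smaller than the shift.
- *That a rise of several points is a treatment bias.* It is a level shift within each arm and largely cancels when oxygen use is similar.
- *That every score-4 patient carries the artefact and no score-3 patient does.* Room air at screening applies only where possible, and a score-3 patient who later needs oxygen is also affected.
- *That score-4 baselines must be 92% or lower.* The scale gives a number (93% and above) only for score 3; score 4 is described without one.

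The main SAP dated 29SEP2023 was not supplied, and the SAP addendum does not mention vital signs. The main SAP may already separate saturation by oxygen use. The Schedule of Events also lists vital signs on Day 1. If a pre-dose Day 1 reading were used as a repeat baseline, its oxygen condition would be unstated, which would not resolve the mismatch.

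**Conclusion.** The mismatch holds on the protocol text. As written, the saturation change table mixes oxygen delivery with lung function. It can build a rise into the results of patients on oxygen and mask worsening in those who start oxygen later.

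The between-arm effect is about 0.3 to 0.6 points for each 10-percentage-point difference in oxygen use, and nil if use is equal. This rests on an assumed constant gain of 3 to 6 points from oxygen; the documents give neither that gain nor oxygen use by arm.

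The Synopsis sentence on changes from baseline covers most safety assessments together and says only that they can show improvement or worsening. It does not make saturation change a measure of efficacy. Severity is minor: a cheap improvement to a descriptive safety table, subject to what the main SAP says.

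**What to change.** First check whether the main SAP already separates saturation by oxygen status. If it does not:

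1. Tabulate saturation and its change from baseline by ordinal score on the day of the reading (3 = no oxygen, 4, 5, 6). Section 10.1 has this score collected daily in hospital. Link on the day that the score describes, since it is assigned the day after.
2. Present change from baseline as like-for-like only for days scored 3. The score is the day's worst status, so a 3 implies no oxygen need that day. Footnote that the baseline is off oxygen only where that was possible.
3. Report the incidence of 92% or lower with the number of patients who had a room-air reading as the denominator.

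Do not build this on in-hospital oxygen flow or a saturation/FiO2 ratio. Section 9.2.3 asks on Days 5, 8, 12 and 14 or discharge only whether oxygen is in use, without naming flow, and has no oxygen item on the other hospital days.

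The cost is one linked table and a footnote, with no new data. There are fewer evaluable pairs, and the match is approximate at scores 4 and above, because a day's worst status need not apply at the time of each reading. The groups are defined after randomisation, so the table must stay descriptive. The addendum records that results were first released on 14MAR2024, so the table should be labelled as added afterwards.

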Any AE that occurs from the first dose of study treatment (or prior to the first dose of study treatment, and worsening after first dose of study treatment) until the End-of-Study follow-up, on Day 60, or until early termination or death, whichever occurs first, will be considered treatment emergent (TEAE) and must be recorded in the CRF and, if an SAE, reported immediately to the Sponsor. Adverse events that are ongoing at the end of the follow-up period should be marked as ongoing. However, it is the responsibility of the Investigator to follow up on these events until resolution, where possible, according to standard medical care.

Any AE or SAE that the investigator becomes aware of outside of the reporting period until the end of the study participation of a patient that has or is believed to have a causal relationship to the study drug should be reported to Laurent Pharmaceuticals via telephone. Patients who experience AEs will be monitored with relevant clinical assessments and laboratory tests, as determined by the Investigator. All AEs and laboratory abnormalities encountered during the study should be followed until resolution or stabilization of the event(s). Any action taken and follow-up results must be recorded in the patient's medical record. Follow-up laboratory results should be filed with the patient's source documentation and CRF. For all AEs that require the patient to discontinue treatment, relevant clinical assessments and laboratory tests should be performed until final resolution or stabilization of the event(s). These assessments should be captured in the source data and SAE forms but will not be entered in the CRF.

Due to the critical nature of the COVID-19 infection and its expected complications in mechanically ventilated patients, a revised definition of reportable adverse events (AEs) was developed for use following the Canadian guidelines for AE/SAE reporting in academic critical care trials ⁴. The following 2 categories of events will therefore not be reported in the eCRF:

- Any expected adverse complications related to treatments/procedures commonly administered in the context of invasive mechanical ventilation, such as right main bronchus intubation, lacerated lips, tongue, pharynx and trachea, vocal cord injury, chipped teeth, aspiration, introduction of infection, airway obstruction, hypoxia, hypotension, and cardiac arrhythmias.

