11.1.2 Clinically Significant Assessments

Study assessments including laboratory tests and vital signs should be assessed and those deemed a clinically significant worsening from baseline documented as an AE. When possible, a clinical diagnosis for the study assessment should be provided rather than the abnormal test result alone (e.g. urinary tract infection, anemia). In the absence of a diagnosis, the abnormal study assessment itself should be listed as the AE (e.g. bacteria in urine or decreased hemoglobin).

An abnormal study assessment is considered clinically significant if the patient has one or more of the following:

- Concomitant signs or symptoms related to the abnormal study assessment;
- Further diagnostic testing or medical/surgical intervention;
- A change in the dose of study drug or discontinuation from study drug treatment.

Repeat testing to determine whether the result is abnormal, in the absence of any of the above criteria, does not necessarily meet clinically significant criteria. The determination of whether the study assessment results are clinically significant must be made by the Investigator. A laboratory abnormality judged to be Grade 4, in itself, may not constitute an SAE unless the clinical status of the patient indicates a life-threatening AE.

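### Protocol section 12.8.3 repeats the low-diastolic criterion in the systolic bullet, leaving the table of abnormal vital-sign shifts without a low-systolic category

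*Protocol*

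**What the plan says.** Protocol section 12.8.3 plans a by-arm table of "The number and percentage of patients that meet the abnormal criteria for with shift changes from baseline of the vital signs during the TEAE period" and then lists the changes of interest.

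- Diastolic bullet: "Diastolic Blood Pressure ≤45 mmHg and decrease from baseline ≥10 mmHg, Diastolic Blood Pressure ≥110 mmHg and increase from baseline ≥10 mmHg".
- Next bullet, which opens with systolic pressure: "Systolic Blood Pressure ≥160 mmHg and increase from baseline ≥20 mmHg, Diastolic Blood Pressure ≤45 mmHg and decrease from baseline ≥10 mmHg".
- Heart rate bullet: "Heart rate ≤50 bpm and decrease from baseline ≥20 bpm, heart rate ≥120 bpm and increase from baseline ≥20 bpm".

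Temperature has a lower and an upper limit (35°C and 38°C) with no change-from-baseline condition. Oxygen saturation has a lower limit only (92% on room air).

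The same section plans mean, standard deviation, median, minimum and maximum at each time point, and change from baseline by arm. It plans no statistical analysis of vital signs. Section 11.3 confirms that systolic pressure is a study variable: "Vital signs include blood pressure (systolic and diastolic), temperature". No low-systolic limit appears elsewhere in the protocol, and the supplied SAP addendum does not address vital signs.

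**The concern.** The second half of the systolic bullet is the low-diastolic criterion again, in the place where a reader expects a low-systolic one. Programmed from this text, the table would have a redundant row and no category for low systolic pressure.

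The table is there to show how many patients in each arm crossed a fixed limit with a relevant change from baseline. Summary statistics per time point do not give that number. Vital signs are part of the safety assessment listed first among the secondary endpoints in section 7.1.3, and the patients are hospitalized and at risk of deterioration. A gap in the low-pressure direction therefore makes the by-arm safety display less complete.

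**Working it through.** No sample size, power or alpha is involved. The check sets the criteria side by side and tests them on two hypothetical patients.

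**Step 1. List the blood-pressure criteria by variable and direction (section 12.8.3).**

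| Variable | Low | High |
|---|---|---|
| Diastolic (first bullet) | ≤45 mmHg, decrease ≥10 | ≥110 mmHg, increase ≥10 |
| Systolic (second bullet) | none; low diastolic ≤45 mmHg, decrease ≥10 is repeated | ≥160 mmHg, increase ≥20 |
| Heart rate, for comparison | ≤50 bpm, decrease ≥20 | ≥120 bpm, increase ≥20 |

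Four blood-pressure entries minus one duplicate leaves three distinct criteria. Low systolic has none.

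**Step 2. Check how the comma in each bullet reads.** In the diastolic and heart-rate bullets the two halves cannot both be true of one reading (diastolic cannot be ≤45 and ≥110 mmHg), so the comma separates alternatives. The same reading applies to the systolic bullet. Treating its halves as a joint condition would still not supply a low-systolic criterion.

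**Step 3. Test a fall from 130/75 to 80/50 mmHg.**

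- High systolic: 80 is below 160. Not met.
- Low diastolic: the decrease is 75 − 50 = 25 mmHg, which is at least 10, but 50 is above 45. Not met.
- High diastolic: 50 is below 110. Not met.

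Systolic has dropped by 130 − 80 = 50 mmHg and the patient meets no blood-pressure criterion.

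**Step 4. Test a fall from 130/75 to 80/45 mmHg.** Diastolic is 45, which meets ≤45, and the decrease is 75 − 45 = 30 mmHg, which meets ≥10. This patient is counted, but as low diastolic.

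**Step 5. Look for other outputs that would show low systolic pressure.**

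- The descriptive statistics show the lowest value at each time point and the change from baseline. They do not show how many patients had a low value.
- Section 11.1.2 gives an adverse-event route: "Study assessments including laboratory tests and vital signs should be assessed and those deemed a clinically significant worsening from baseline documented as an AE". Section 12.8.1 then gives numbers and percentages of patients by preferred term and arm.
- That route depends on investigator judgment. Section 11.1.1 also narrows it: "airway obstruction, hypoxia, hypotension, and cardiac arrhythmias" are among the expected complications of treatments and procedures around invasive ventilation that are not reported in the eCRF.

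**The case against.** The strongest counter-argument is that this is a copying slip in a descriptive list, and that larger claims built on it fail. Four such claims might be inferred, and the documents support none of them.

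- **All low-systolic shifts go uncounted.** Step 4 shows otherwise. The documents give no data on how many low-systolic patients keep a diastolic above 45 mmHg, so the share missed cannot be stated.
- **Low diastolic is counted twice.** The output is patients meeting a criterion. A repeated criterion gives an identical, redundant row and inflates nothing.
- **This is the only by-arm count of abnormal vital signs.** The adverse-event tables also give counts for clinically significant hypotension, within the limits in step 5.
- **The released tables are wrong.** Section 12 of the protocol leaves methodological detail to the SAP, and the addendum refers to the main SAP of 29 September 2023 for the complete description. That document was not available, and its criteria may be correct.

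It can also be said that a low-systolic limit may never have been intended, since oxygen saturation is also one-directional. This carries less weight. The repeated clause adds nothing to the diastolic bullet, it sits in the systolic bullet, and diastolic pressure, heart rate and temperature each have both directions. The intention remains an inference, though a strong one.

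What stands is the duplicated clause, the absent category, and the fact that the other outputs cover it only in part.

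**Conclusion.** The point holds as a drafting error in a stated analysis rule. Section 12.8.3 as written yields a table with low-diastolic, high-diastolic and high-systolic categories and no low-systolic one. Patients whose systolic pressure falls while diastolic stays above 45 mmHg meet no blood-pressure criterion, in either arm.

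The size is small. One descriptive category is missing, and no endpoint, test or efficacy conclusion is affected. That the clause is a duplicate and that no low-systolic limit exists in the supplied documents is certain. That a low-systolic limit was intended is inferred from the pattern of the list. Whether any table was produced with the slip is unknown without the main SAP and the outputs.

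**What to change.** 1. Compare the bullet with the main SAP of 29 September 2023 and bring the two into agreement.
2. Replace the duplicated clause with the low-systolic criterion the sponsor intended. Both its limit and its decrease from baseline are for the sponsor to state; the documents give no figure and none is proposed here.
3. Tabulate that category by arm next to the other blood-pressure rows.
4. Check whether the existing tables carry the slip. The SAP addendum says the planned analyses were completed after database lock, with results first released on 14 March 2024. If the slip is there, add the row to the CSR and label it as a correction made after database lock.

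The cost is one clause of text and one table row, plus a post-lock output if step 4 applies. The October 2024 addendum already adds CSR tables, so a route exists. Section 12.8.3 already plans blood-pressure summaries, so the row should need no further data. The sponsor should confirm that systolic values were captured, because the visit lists in sections 9.2.1 and 9.2.3 name heart rate, respiratory rate, oxygen saturation and temperature but not blood pressure.

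### The temperature criterion in the vital-signs shift table has no baseline condition, so fever carried over from entry is counted together with new fever

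*Protocol*

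**What the plan says.** Section 12.8.3 of the protocol promises, by treatment group, the number and percentage of patients who "meet the abnormal criteria for with shift changes from baseline of the vital signs" in the treatment-emergent period. The items that follow are described as changes of interest:

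- **Diastolic pressure:** limit plus change, for example "Diastolic Blood Pressure ≤45 mmHg and decrease from baseline ≥10 mmHg".
- **Systolic pressure:** limit plus change, "Systolic Blood Pressure ≥160 mmHg and increase from baseline ≥20 mmHg".
- **Heart rate:** limit plus change, for example "Heart rate ≤50 bpm and decrease from baseline ≥20 bpm".
- **Temperature:** limits only, "Temperature ≤35°C and ≥38°C".
- **Oxygen saturation:** besides values the investigator judges abnormal and reports as adverse events, a limit only: "the incidence of oxygen saturation being 92% or lower when measured in patient stabilized on room air, will be presented by treatment group".

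The same section also presents change from baseline for every vital sign and states that vital signs will not be analysed statistically. Section 12 defines baseline as the screening value, unless a permitted repeat was obtained before the first dose. Section 9.2.1 collects body temperature at screening.

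**The concern.** The introduction announces shifts, but the temperature item describes a state. Temperature is also a vital sign that the disease itself can make abnormal at entry: fever is on the screening symptom check in section 9.2.1, and section 11.3 describes "temperature (oral or tympanic, consistently determined being a key COVID-19 sign". Section 9.2.3 asks for vital signs at least twice a day on most hospital days, so a resolving fever has several chances to produce one reading of 38°C or more after the first dose. That patient enters the count while improving.

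This differs from the protocol's own idea of treatment emergence in section 12.8.1, where an event must appear or become more severe after the first dose. A count that mixes carried-over fever with new fever is a weaker safety display. A real difference between arms in new fever would look smaller, in relative terms, than it is.

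**Working it through.** **Comparison of the items.** The blood pressure and heart rate criteria all carry a minimum change (10 mmHg diastolic, 20 mmHg systolic, 20 bpm). Two numeric items carry none: temperature, and saturation of 92% or lower on room air. No single reading can be both at or below 35°C and at or above 38°C, so the temperature bullet has to mean two limits. The text does not say whether they form one count or two.

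**Size.** The plan states no figure to reproduce and gives no rate of fever at entry or on treatment. The inputs below are assumptions.

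- f = share febrile at baseline: 10% or 25%.
- s = share of those with a reading of 38°C or more after the first dose: 30%, 50% or 100%.
- b = f × s = share counted because of carried-over fever, taken as equal in the two arms.
- p = rate of new fever among all other patients: 15% v 5%, a true ratio of 3 and a true difference of 10 points.

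Proportion counted = b + (1 − b) × p.

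Example, f = 10% and s = 30%: b = 0.03. One arm shows 0.03 + 0.97 × 0.15 = 17.6%, the other 0.03 + 0.97 × 0.05 = 7.9%, and the ratio is 2.2.

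| f | s | b | Counted, higher v lower arm | Ratio | Difference (points) |
|---|---|---|---|---|---|
| 10% | 30% | 3% | 17.6% v 7.9% | 2.2 | 9.7 |
| 10% | 50% | 5% | 19.3% v 9.8% | 2.0 | 9.5 |
| 10% | 100% | 10% | 23.5% v 14.5% | 1.6 | 9.0 |
| 25% | 30% | 7.5% | 21.4% v 12.1% | 1.8 | 9.3 |
| 25% | 50% | 12.5% | 25.6% v 16.9% | 1.5 | 8.8 |
| 25% | 100% | 25% | 36.3% v 28.8% | 1.3 | 7.5 |

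With a smaller assumed effect, 10% v 5%, a true ratio of 2.00 falls to 1.31 at b = 10% and 1.07 at b = 40%; the difference falls from 5.0 to 4.5 and 3.0 points.

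**What does not depend on the inputs.** If b is equal in the arms, the difference shown is (1 − b) times the true difference, and the ratio moves towards 1 as b rises. The ratio suffers much more than the difference.

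**The case against.** The strongest reply is that little depends on this table. It is descriptive. Change from baseline in temperature is shown by arm, and worsening of a vital sign that the investigator judges clinically significant becomes an adverse event (section 11.1.2), tabulated as treatment-emergent under section 12.8.1. This stands and limits the importance of the point. It does not replace the count: a mean change averages falling entry fevers with new ones, and the adverse-event route depends on investigator judgement.

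A second reply is that a shift in a categorical limit ordinarily means moving from within the limit to beyond it, so the introduction may already exclude patients febrile at baseline. That reading is possible, but the other items spell out their baseline condition and temperature does not, so the programmer has to guess. The full SAP dated 29SEP2023 is not among the documents reviewed, only its addendum; a clarification there cannot be excluded.

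Third, the inputs are assumed. That is correct. Full persistence is the worst case, which is why a range is shown.

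A reader might also infer more than the text supports:

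- *Temperature is the only numeric item without a baseline condition.* The saturation limit lacks one too.
- *Everyone febrile at entry is counted.* A qualifying reading in the treatment-emergent period is also needed.
- *Entry fever hides new hypothermia.* That follows only if the two limits are pooled. The blood pressure and heart rate items list low and high criteria separately, so two counts is the more natural reading.
- *The count mostly measures entry fever.* That depends on the assumed rates; fever on a symptom checklist does not show how common it is at entry.

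**Conclusion.** The point holds as a minor defect in specification. Unlike blood pressure and heart rate, temperature has no stated baseline condition, so entry fever that persists past the first dose is counted with new fever.

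On the assumed 15% v 5%, a true ratio of 3 would appear as about 2.2 to 1.6 with 10% febrile at entry and 1.8 to 1.3 with 25%, across 30% to 100% persistence. This assumes equal carry-over in both arms. The direction is then certain; the size is not known from the documents. No efficacy result and no planned test is affected.

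**What to change.** Replace the temperature bullet with two separately reported counts by arm:

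1. A reading of 38°C or more among patients below 38°C at baseline.
2. A reading of 35°C or less among patients above 35°C at baseline.

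Use each baseline group as the denominator. A minimum change from baseline added to each limit, as for heart rate, would also bring the bullet into line with the others. It would help to state in the same place whether the saturation count includes patients already at or below its limit at entry.

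The cost is a line of wording and a small table; screening temperature is already collected. The downside is a slightly smaller denominator for the fever count: with 132 per arm, 132 × 0.90 ≈ 119 or 132 × 0.75 = 99 under the two assumed rates. The addendum records that results were first released on 14MAR2024 and already adds tables to the study report, so this could be one more additional table, labelled as specified after that release.
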